- ✓ Treatment period Phase 1: From completion of scheduled tests for the first day of the treatment period to completion of scheduled tests for Week 24 of the treatment period
- ✓ Treatment period Phase 2: From completion of tests specified for Week 24 of treatment period to completion of tests specified for Week 52 of treatment period

Subjects will be randomly allocated to the MT-6548 group or the darbepoetin group on the first day of the treatment period. Allocation ratios will be 1:1 for both groups.

Stratification factors are as below.

- ✓ Correction cohort or conversion cohort
- ✓ Mean Hb during screening period (mean of latest two measurements from central testing facility):
 - Correction cohort: <10.0 g/dL or ≥ 10.0 g/dL
 - Conversion cohort: <11.0 g/dL or ≥ 11.0 g/dL

Treatment period study visits will be made every 2 weeks up until Week 12, and every 4 weeks thereafter for scheduled tests. However, study visits may be more frequent if variation in Hb levels causes concern for excessive increase or decrease in Hb, if the dose interval for darbepoetin alfa injection is shorter than the study visit interval, or for other reasons.

(3) Follow-up observation period

The follow-up observation period consists of 2 weeks from completion of blood sampling for haematology tests on the final day of the treatment period. The final day of the follow-up

observation period is 2 weeks from the completion of blood sampling for haematology tests on the final day of the treatment period, regardless of whether a study visit is made on that day.

Subjects should make study visits as close to the same time as possible during the study period for scheduled tests.

5. Study drug, dosage, and administration

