5.2 Study design

The current study is a multicenter, randomized, open-label, active-controlled, parallel group comparative study.

(1) Screening period

The screening period begins on the first day of the screening period, and ends upon completion of tests required on the first day of the treatment period. Maximum screening period time is 6 weeks. Two visits will be made during the screening period; the first (SV1) is the first day of the screening period. The second screening period visit (SV2) occurs after results from laboratory tests performed on the first day of the screening period have been obtained. Re-testing will be performed as necessary.

(2) Treatment period

The treatment period will last from completion of scheduled tests on the first day of the treatment period to completion of blood sampling for haematology tests on the final day of the treatment period (Week 52 of the treatment period or discontinuation of treatment).

The treatment period consists of phase 1 and phase 2, as defined below.

- ✓ Treatment period Phase 1: From completion of scheduled tests for the first day of the treatment period to completion of scheduled tests for Week 24 of the treatment period
- ✓ Treatment period Phase 2: From completion of tests specified for Week 24 of treatment period to completion of tests specified for Week 52 of treatment period

Treatment period study visits will be made every 2 weeks up until Week 12, and every 4 weeks thereafter for scheduled tests. However, study visits may be more frequent if variation in Hb levels causes concern for excessive increase or decrease in Hb, if the dose interval for darbepoetin alfa injection is shorter than the study visit interval, or for other reasons.

(3) Follow-up observation period

The follow-up observation period consists of 2 weeks from completion of blood sampling for haematology tests on the final day of the treatment period. The final day of the follow-up observation period is 2 weeks from the completion of blood sampling for haematology tests on the final day of the treatment period, regardless of whether a study visit is made on that day.

Subjects should make study visits as close to the same time as possible during the study period for scheduled tests.

Rationale

Screening period: Established to confirm subject suitability for the study.

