4.9 Mean daily dose/mean weekly dose

Mean daily dose of MT-6548 during each scheduled study visit period* = Daily dose based on the physician's prescription \times Period of administration (days)^{*3} of the corresponding dose^{*2} between the scheduled study visits*/Period between the schedule study visits (days)^{*4}.

Mean weekly dose of darbepoetin alfa during each scheduled study visit period* = (Daily dose based on the physician's prescription \times Period of administration (days)^{*5} of the corresponding dose^{*2} between the scheduled study visits*/Period between the scheduled study visits (days)^{*4}) \times 7.

*: For each period between the scheduled study visits, the actual study visit dates will not be considered, and this variable should be fixed as follows:

- ✓ The first day of the treatment period to Week 2 of the treatment period: The first day of the treatment period (Day 1) to Day 14
- ✓ Week 2 of the treatment period to Week 4 of the treatment period: Day 15 to Day 28
- ✓ The same should apply thereafter, and the final period between the scheduled study visits should be Week 48 to Week 52 of the treatment period: Day 337 to the day before the day of blood sampling for hematological tests at Week 52 of the treatment period.

However, for subjects who discontinued their treatment, the final period between the scheduled study visits should be up to the day before discontinuation.

*²: If there are multiple applicable doses, the sum of the calculated values for each dose should be used.

*³: The number of days without drug administration other than drug interruption should not be excluded from the “period of administration (days)”.

*⁴: 14 days up to Week 12 of the treatment period and 28 days after Week 12 of the treatment period.

However, for subjects who discontinued their treatment, the final period between the scheduled study visits (days) should be the actual number of days until the day before discontinuation.

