4.11 Iron supplement dosage

The dose of iron supplements is defined by the following formula. However, the dose of iron supplements will not be calculated if iron supplements are used as needed.

Mean monthly dose of iron supplements during the screening period* and each scheduled study visit period*² (tabulation period of iron supplements) = (Daily dose based on the physician's prescription × Period of administration (days) of the corresponding dose^{*3} during the tabulation period of iron supplements)/Tabulation period of iron supplements (days)^{*4} × 30.4375^{*5}

*: The number of days of the screening period is “First day of the treatment period – First day of the screening period”.

*²: For each period between the scheduled study visits, the actual study visit dates are not considered, and this tabulation is fixed as follows:

- ✓ The first day of the treatment period to Week 2 of the treatment period: The first day of the treatment period (1 day) to 14 days.
- ✓ Week 2 of the treatment period to Week 4 of the treatment period: 15 to 28 days.
- ✓ The same should apply thereafter, and the final period between the scheduled study visits should be Week 48 to Week 52 of the treatment period: 337 days to the day before the day of blood sampling for hematological tests at Week 52 of the treatment period. However, for subjects who discontinued their treatment, the final period between the scheduled study visits should be up to the day before discontinuation.

*³: If there are multiple applicable doses, the sum of the calculated values for each dose should be used.

*⁴: For subjects who discontinued their treatment, the final period between the scheduled study visits (days) should be the actual number of days until the day before discontinuation.

*⁵: In this tabulation, 1 month is counted as 30.4375 days (365.25/12 = 30.4375).

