(4) Proportion of subjects receiving rescue therapy with ESA formulations, red blood cell transfusion, or phlebotomy

The number and proportion of subjects and the 95% CI (Clopper-Pearson [Exact] method) for the proportion of subjects receiving rescue therapy with an ESA preparation should be provided by treatment group, after the first day of the treatment period, in each period between scheduled study visits and during the entire treatment period from the first day to Week 52 of the treatment period.

The estimate, its 95% CI (exact method), and p-value (Fisher's exact test) for between-group difference (MT-6548 – darbepoetin) should be calculated for the proportion of subjects receiving rescue therapy.

The analyses same to the above subjects receiving rescue therapy with ESA formulation should be performed for subjects receiving rescue therapy with RBC transfusion or receiving phlebotomy.

(5) Study drug dosage

1) Study drug dosage

Descriptive statistics of the average daily dose of MT-6548 and mean weekly dose of darbepoetin alfa injection (recombinant) should be calculated, after the first day of the treatment period, in each period between scheduled study visits and during the entire treatment period from the first day to Week 52 of the treatment period. The time course diagram for mean daily dose of MT-6548 and mean weekly dose of darbepoetin alfa injection (recombinant) should be separately prepared by treatment group. 95% CI of the mean will be represented by an error bar. Each period between scheduled study visits is defined as the period between the scheduled visit and the day before the next scheduled visit.

2) Distribution of MT-6548 tablets and darbepoetin alfa injection

The number and proportion of subjects and the 95% CI (Clopper-Pearson [Exact] method) of proportion per daily dose of MT-6548 tablets and per weekly dose of darbepoetin alfa (recombinant) during the treatment period should be provided by treatment group.

The proportion of subjects receiving each dose of MT-6548 tablets and darbepoetin alfa injection (recombinant) at each evaluation time point of the treatment period should be provided as a stacked bar graph with the number of subjects in each treatment group as 100%. Stacked bar charts should be generated separately for each treatment group.

If no prescription is available on the day of each evaluation timepoint of the treatment period, the dose should be based on the immediately before prescription.

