Descriptive statistics of the change in the mean dose of iron supplement per month from the baseline (mean dose of iron during the screening period) should be calculated, after the first day of the treatment

period, in each period between scheduled study visits and during the entire treatment period from the first day to Week 52 of the treatment period. Before and after comparison should be conducted for changes from baseline using the paired t-test. The changes should be compared between groups using the Student-t test. The mean value of the between-group difference (MT-6548 – darbepoetin), its two-sided 95% CI, t-statistic, and p-value should be provided.

The dosage of iron supplement should be calculated using the dose as iron.

If no iron supplement is administered, the dose should be tabulated as 0 mg. Subjects who changed the administration route of an iron supplement during the treatment period and subjects who had never received an iron supplement during the treatment period should be excluded from the tabulation.

(8) Proportion of subjects receiving oral, intravenous, or (any route) administration of iron supplements

The number and proportion of subjects and the 95% CI (Clopper-Pearson [Exact] method) for the proportion of subjects treated with oral, intravenous, or oral iron supplement (any route) should be provided by treatment group for screening period, and after the first day of the treatment period, in each period between scheduled study visits and during the entire treatment period from the first day to Week 52 of the treatment period. McNemar tests should be used to compare baseline values (proportion of subjects receiving iron supplements by the aforementioned route in the screening period) with those before and after each period between scheduled study visits. The estimate, its 95% CI (exact method), and p-value (Fisher's exact test) for between-group difference (MT-6548 – darbepoetin) should be calculated for the proportion of subjects receiving oral, intravenous, or (any route) iron supplement.

Subjects who have not received an iron supplement are to be subjects who have never received an iron supplement during the relevant period, and subjects who have received an oral, intravenous, or (any route) iron supplement are to be subjects who have received an iron supplement at least once during the relevant period.

(9) Proportion of subjects with serum ferritin values of ≥ 100 ng/mL or TSAT of $\geq 20\%$.

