Descriptive statistics of the change in the mean dose of iron supplement per month from the baseline (mean dose of iron during the screening period) should be calculated, after the first day of the treatment period, in each period between scheduled study visits and during the entire treatment period from the first day to Week 24 of the treatment period. Before and after comparison should be conducted for changes from baseline using the paired t-test. The changes should be compared between groups using the Student-t test. The mean value of the between-group difference (MT-6548 – darbepoetin), its two-sided 95% confidence interval, t-statistic, and p-value should be provided.

The dosage of iron supplement should be calculated using the dose as iron.

Confidential

If no iron supplement is administered, the dose should be tabulated as 0 mg. Subjects who changed the administration route of an iron supplement during the treatment period and subjects who had never received an iron supplement during the treatment period should be excluded from the tabulation.

(8) Proportion of subjects receiving oral, intravenous, or (any route) administration of iron supplements

The number and proportion of subjects and the 95% confidence interval (Clopper-Pearson [Exact] method) for the proportion of subjects treated with oral, intravenous, or oral iron supplement (any route) should be provided by treatment group for screening period, and after the first day of the treatment period, in each period between scheduled study visits and during the entire treatment period from the first day to Week 24 of the treatment period. A McNemar test should be used for before and after comparison between baseline (ratio of subjects receiving iron supplements by the aforementioned route in screening period) and each period between scheduled study visits. The estimate, its 95% CI (exact method), and p-value (Fisher's exact test) for between-group difference (MT-6548 – darbepoetin) should be calculated for the proportion of subjects receiving oral, intravenous, or (any route) iron supplement.

Subjects who have not received an iron supplement are to be subjects who have never received an iron supplement during the relevant period, and subjects who have received an oral, intravenous, or (any route) iron supplement are to be subjects who have received an iron supplement at least once during the relevant period.

(9) Proportion of subjects with serum ferritin ≥ 100 ng/mL or TSAT $\geq 20\%$.

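### Within-arm McNemar tests on iron use compare windows of unequal length, so intermittent iron can appear to fall or rise when use is constant

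*SAP*

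**What the plan says.** Final SAP 8.5.2(8) tabulates the proportion of subjects on oral, intravenous or any-route iron in screening, in each period between scheduled visits and over the whole treatment period. Users are defined as "subjects who have received an iron supplement at least once during the relevant period". The within-arm test is given as "McNemar tests should be used to compare baseline values (proportion of subjects receiving iron supplements by the aforementioned route in the screening period". The rest of that sentence is unclear in translation, but Phase 1 SAP 8.5.3(8) settles the meaning: "A McNemar test should be used for before and after comparison between baseline (ratio of subjects receiving iron supplements by the aforementioned route", set against each period between scheduled visits. Final SAP 8.7.2 repeats the rule for the Phase 1 re-tabulation.

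The windows differ in length:

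- **Screening.** Protocol 5.2 says "Maximum screening period time is 6 weeks" and gives no minimum. For iron dose, Final SAP 4.11 sets the length as the first treatment day minus the first screening day, so it varies by subject.
- **Treatment periods.** The protocol's visit schedule is "Treatment period study visits will be made every 2 weeks up until Week 12, and every 4 weeks thereafter for scheduled tests". Final SAP 4.11 fixes the iron periods to match: Days 1 to 14, 15 to 28 and so on, the last starting at Day 337. Final SAP 4.9 states the same lengths for study-drug dose: "14 days up to Week 12 of the treatment period and 28 days after Week 12 of the treatment period".

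No rule equalises or adjusts for window length in endpoint (8). The neighbouring iron-dose endpoint (7) is divided by days and scaled to a 30.4375-day month.

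**The concern.** For any treatment that is not continuous, the chance of at least one administration rises with the length of the window. McNemar's null hypothesis is that the two paired proportions are equal. If one window is longer, that hypothesis is false for intermittent users even when practice has not changed, and the p-value reflects window length as well as iron use.

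Intermittent use is foreseeable. Protocol 8.5.2 has iron given to maintain ferritin or TSAT, with dose and route left to the investigator, and the SAP tabulates intravenous iron separately. At stake is a within-arm statement that iron use fell, or rose, after the start of study treatment when only the counting window had changed. There are six consecutive 14-day periods before Week 12, so the artefact could look like a consistent pattern.

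**Working it through.** The documents give no figure for this comparison, so there is none to reproduce.

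**Inputs from the documents.** Screening S of at most 42 days; periods T of 14 days to Week 12 and 28 days afterwards; a user is anyone with at least one administration in the window; two-sided 5% level (Final SAP 8.1.1); 150 subjects per arm (Final SAP 2.5).

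**Assumptions, not in the documents.** Mean dosing interval v of 4, 8 or 12 weeks; constant use; 15, 30 or 60 intermittent users per arm; S of 14, 28 or 42 days.

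**Step 1: chance of being counted.** For random dosing it is 1 − exp(−T/v). For regular dosing with a random starting point it is min(1, T/v). With v = 28 days and random dosing: 1 − exp(−42/28) = 77.7%, 1 − exp(−14/28) = 39.3%, 1 − exp(−28/28) = 63.2%.

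| Dosing at constant use | 42-day screening | 14-day period | 28-day period |
|---|---|---|---|
| Random, 4-week mean | 77.7% | 39.3% | 63.2% |
| Random, 8-week mean | 52.8% | 22.1% | 39.3% |
| Random, 12-week mean | 39.3% | 15.4% | 28.3% |
| Regular, every 4 weeks | 100% | 50% | 100% |
| Regular, every 8 weeks | 75% | 25% | 50% |
| Daily oral | 100% | 100% | 100% |

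The last two columns show the step at Week 12. It does not involve screening, so it appears whatever the screening length.

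**Step 2: direction of the test.** Against a 14-day period the bias is towards a fall when S exceeds 14 days. Against a 28-day period it is towards a fall when S exceeds 28 days and towards a rise when S is under 28 days. A subject screened for between 14 and 28 days contributes to a fall before Week 12 and to a rise after it.

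**Step 3: one worked case.** Take 30 users, regular 4-weekly iron, and S of at least 28 days. Screening catches all 30 and a 14-day period catches 15 on average. Discordant pairs are 15 against 0: exact p = 2 × 0.5^15 = 0.00006; chi-square = 15²/15 = 15, p = 0.0001. In the same case a 28-day period also catches all 30, so there is no signal after Week 12.

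**Step 4: false-signal rates.** Exact two-sided McNemar test, random dosing at a 4-week mean, no true change, 2,000 runs, one period tested:

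| Comparison | 15 users | 30 users | 60 users |
|---|---|---|---|
| 42-day screening v 14-day period (fall) | 40% | 79% | 99% |
| 28-day screening v 14-day period (fall) | 13% | 37% | 67% |
| 42-day screening v 28-day period (fall) | 6% | 15% | 31% |
| 14-day screening v 28-day period (rise) | not shown | 37% | 68% |
| Equal windows, 14 or 28 days (either direction) | 1.4–1.7% | 2.2–2.4% | 3.0–3.2% |

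With 14-day screening against a 14-day period, both proportions are 39.3% and there is no bias.

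**The case against.** The strongest reply is that this is an exploratory corner of the plan with sound analyses beside it. Phase 1 SAP 8.5.4.7 calls the secondary and other endpoints exploratory. The same paragraph of Final SAP 8.5.2(8) provides a between-arm difference with an exact interval and Fisher's test. It also gives proportions over the whole treatment period. Protocol 10.1.3(8) asks only for cumulative intravenous-iron ratios to Weeks 24 and 52. The documents give no dosing frequency or number of intravenous users, so the real effect could be negligible, and they give only a maximum for screening. All of this stands, and it limits the point to the within-arm p-values and the reading of the period-by-period table.

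Three stronger readings are tempting, and the documents do not support them.

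- **That the tests will declare a rise after Week 12.** No planned test compares later with earlier treatment periods; every McNemar test is against screening. A rise against screening needs screening shorter than 28 days.
- **That iron use will always seem to fall at the start of treatment.** That needs screening longer than 14 days and dosing less often than every 2 weeks.
- **That the artefact could favour one drug.** Both arms share the same planned windows, so it would appear in both and does not bias the Fisher comparison.

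**Conclusion.** The rule is wrong as written, in a narrow place. For intermittent, mainly intravenous, iron given less often than every 2 weeks, the within-arm McNemar tests mix window length with iron use, and the table steps up at Week 12 for the same reason. The direction follows from the documents once a subject's screening length is known. The net effect in an arm depends on the mix of screening lengths.

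The size does not follow from the documents. It ranges from nothing (daily oral iron, or 14-day screening against 14-day periods) to a near-certain false fall (60 users, 42-day screening, 4-week mean interval). The length-scaled iron dose, the cumulative proportions, the between-arm comparison within a period and the primary non-inferiority conclusion are untouched. This is a low-priority correction, worth making because it is cheap.

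**What to change.** In Final SAP 8.5.2(8) and 8.7.2 and Phase 1 SAP 8.5.3(8), restrict McNemar tests to windows of equal length, in one of two ways:

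1. Compare the last 14 days of screening with the 14-day periods to Week 12, and the last 28 days of screening with the 28-day periods afterwards.
2. Use 28-day windows throughout, joining the 14-day periods in pairs before Week 12, against the last 28 days of screening.

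In both, include only subjects with enough recorded screening days and report how many there are. The restriction is needed because Protocol 8.5.4 requires iron to be recorded from screening onward, so earlier use cannot be assumed available. A rate of administrations per 4 weeks cannot replace the missing days, because McNemar needs a yes/no variable.

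Otherwise omit the McNemar tests; the cumulative ratios that the protocol asks for would remain. Wherever the 14-day and 28-day periods are tabulated together, add a footnote on the change of window length at Week 12.

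The cost is SAP wording and re-binning of recorded dates, with fewer subjects in the within-arm test under either option and, under the second, a coarser early time course.
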